Abbreviated Title: Image guided radiation
Version Date: 06/03/2024

Abbreviated Title: Image guided radiation
NIH Protocol #: 18-C-0028
Version Date: 06/03/2024
NCT Number: NCT03388619

Title: A Phase I Trial of Highly Conformal, Hypofractionated, Focally Dose Escalated Post-Prostatectomy Radiotherapy

NCI Principal Investigator: [name]
Radiation Oncology Branch (ROB)
Center for Cancer Research (CCR)
National Cancer Institute (NCI)
National Institutes of Health (NIH)
[name]
[name]
[name]
[contact]
E-mail: [contact]

Commercial Devices:

Radiation

PRÉCIS

Background:

Prostate cancer that recurs after prostatectomy (rising PSA) with no evidence of metastatic disease is often treated with radiation to the entire prostate bed to a dose of 66-72 Gy over 6-7 weeks. This treatment can provide PSA control in approximately 75% of patients, but may have associated genitourinary and gastrointestinal toxicity due to irradiation of the rectum, small bowel, and bladder. Imaging of prostate cancer has improved to the extent that recurrent disease is often identified in the prostate bed or in other pelvic sites. The current standard is to irradiate the entire prostate bed to the total dose. This trial will test the tolerability of accelerated treatment designed to yield a similar rate of late toxicity. In addition, in patients with visible tumor, it will test the feasibility of delivering a lower dose to the prostate bed and an integrated boost (simultaneous) to the visible tumor to allow a higher dose to visible tumor than can be delivered with standard approaches.

Objective:

- Define the maximum tolerated dose (MTD) hypofractionation of image guided, focally dose escalated post-prostatectomy radiation.

Eligibility:

- PSA recurrence after prostatectomy or indications for adjuvant radiation after prostatectomy.
- No evidence of distant metastases of prostate cancer (pelvic lymph nodes are allowed).
- Age ≥ 18 years old
- ECOG performance status ≤ 1

Design:

National Institutes of Health (NIH)-funded investigators and clinical trial site staff who are responsible for the conduct, management, or oversight of NIH-funded clinical trials have completed Human Subjects Protection and ICH GCP Training.

The protocol, informed consent form(s), recruitment materials, and all participant materials will be submitted to the Institutional Review Board (IRB) for review and approval. Approval of both the protocol and the consent form must be obtained before any participant is enrolled. Any amendment to the protocol will require review and approval by the IRB before the changes are implemented to the study. In addition, all changes to the consent form will be IRB-approved; an IRB determination will be made regarding whether a new consent needs to be obtained from participants who provided consent, using a previously approved consent form.

1 INTRODUCTION

1.1 STUDY OBJECTIVES

1.1.1 Primary Objective

- Define the maximum tolerated dose (MTD) hypofractionated of image guided, focally dose escalated post-prostatectomy radiation.

1.1.2 Secondary Objectives

- To evaluate the safety and tolerability of the image guided, hypofractionated, focally dose escalated post-prostatectomy radiation.
- Estimate the rate of PSA control (biochemical progression free survival (bPFS) at 1 and 2 years after treatment with image guided, hypofractionated, focally dose escalated post-prostatectomy radiation).
- Describe the effects of image-guided, focally dose escalated prostate bed radiation on patient reported outcomes (SHIM, AUA Symptom Index, EPIC-26).

1.1.3 Exploratory Objectives

- Evaluate decision regret at the time of enrollment and at the end of follow up relating to the primary treatment for prostate cancer to determine if successful salvage mitigates decision regret.
- Explore candidate biomarkers of radiation toxicity in blood and urine of patients receiving image-guided, hypofractionated, focally dose escalated post-prostatectomy radiation.
- Explore MRI imaging parameters of erectile tissues in regard to testosterone and erectile dysfunction
- To compare dosimetry of standard compared to biological optimization algorithms for treatment planning of post-prostatectomy radiation.
- Explore changes in circulating T-cell subsets, circulating T-cell polarization, and circulating myeloid lineages during and after treatment with radiation.
- Evaluate the feasibility of a patient specific circulating DNA copy number analysis for predicting biochemical recurrence
- Explore changes in circulating exosome cargo before, during, and after a course of radiotherapy.

1.2 BACKGROUND AND RATIONALE

1.2.1 Post prostatectomy radiation

Prostate cancer is one of the most common malignancies in men in the United States, with an estimated 161,360 new cases and 26,730 deaths in 2017 [1]. Localized prostate cancer is often treated with radiotherapy or prostatectomy. Both treatments can be exceptionally effective for patients with low grade cancers or low pre-treatment PSA values. In patients with intermediate or high grade tumors (Gleason 7-10), histologic variants, locally advanced disease (disease that has spread beyond the prostate capsule or into the seminal vesicles), or a high pretreatment PSA, the rate of recurrence after potentially curative treatment, such as radiation or surgery, can be

much higher. Long term follow up of patients treated with prostatectomy have yielded 10 year recurrence free rates of 68% [2]. Subsets of patients at highest risk of failure can benefit from post-operative radiation to the prostate bed, even in the absence of a detectable PSA. When given in the absence of a PSA recurrence, the treatment is termed “adjuvant radiation.” Adjuvant radiation, given for high risk features such as seminal vesicle invasion, extra prostatic spread, or positive margin, has been shown to improve progression free survival and improve the overall survival of prostate cancer patients when compared to observation [3-6].

One concern with the use of adjuvant radiation is that some patients with high risk features will never develop PSA recurrence. Therefore, the benefit of post-prostatectomy radiation may be limited to those destined for eventual PSA recurrence, while many other patients receiving the treatment would never benefit. Thus, many patients with indications for adjuvant radiation after prostatectomy are instead monitored carefully after surgery for evidence of PSA recurrence. If the PSA rises after a prostatectomy and there is no evidence of extra-pelvic metastatic disease, patients are treated with radiotherapy to the prostate bed with curative intent, also known as “salvage” radiotherapy. Treatment with post-operative radiotherapy in the setting of PSA recurrence after radiation yields a 5 year progression free survival of 62-80%[7]. Comparisons of adjuvant and salvage radiation are currently ongoing [8], however both are considered reasonable options as per the current standard of care.

The volumes targeted by irradiation in the post-prostatectomy setting (adjuvant or salvage) are relatively standard and have been arrived at by consensus [9]. In general, the remaining seminal vesicles, if any, and the bed of the prostate are included. In some cases, a portion of the pelvic lymph nodes are included. Most commonly, this region receives a total dose of 66 to 72 Gy in 1.8- 2 Gy fractions, given daily Monday through Friday, over 6-7 weeks. Although these treatments are delivered on an outpatient basis, they are a substantial investment of time and may require time away from work and incur transportation costs.

In general, the use of adjuvant and salvage radiation is well tolerated, however a subset of patients will develop acute (during or within 90 days of radiation) or late (more than 90 days after completion of radiation) toxicity. Two recently published randomized trials provide estimates of toxicity with contemporary irradiation techniques [7, 10]. Grade 2 or higher acute genitourinary toxicity occurs in approximately 14% of patients, whereas Grade 2 or higher acute gastrointestinal toxicity occurs in 21% of patients (acute Grade 3 or higher GU and GI, 2% and 0.5% respectively). Grade 2 or higher late genitourinary toxicity occurs in approximately 25% of patients, whereas Grade 2 or higher late gastrointestinal toxicity occurs in 18% of patients (late Grade 3 or higher GU and GI, 7% and 2% respectively).

Radiation is often combined with androgen deprivation therapy (ADT) in patients with prostate cancer treated with salvage radiation after prostatectomy (detectable PSA). Two recently reported randomized trials of salvage radiation after prostatectomy delivered with or without ADT have shown a benefit in progression free survival or overall survival [7, 10]. These trials demonstrated no increase in bowel or bladder toxicity with the addition of ADT to radiation compared to radiation alone. Based on these results, the use of ADT with radiation is considered appropriate in some, but not all, patients receiving salvage radiation. The use of ADT is dependent of specific tumor and patient characteristics, including age, comorbidity, PSA at the time of radiation, Gleason score, margin status, presence of extra prostatic extension, and patient willingness. We will allow patients to receive ADT on this trial if deemed clinically appropriate,

as the bulk of data suggests that it has no impact on the toxicities we have defined as DLTs in this trial.

1.2.2 Hypofractionation in prostate cancer

Hypofractionation in radiotherapy is the use of fractional doses larger than the “standard” 1.8 Gy – 2 Gy fractions size, with the total dose delivered in a more rapid time frame. Hypofractionated approaches have long been used in the palliative setting to rapidly complete treatment in patients with limited life expectancies. The capacity to utilize modern advanced radiation techniques, such as intensity modulated radiation therapy and stereotactic body radiation therapy, to maximally treat tumor while minimizing the exposure of normal tissues to high doses has led to increased interest in hypofractionated approaches.

For certain cancers, the growth kinetics and radiation response further support the use of hypofractionated approaches over “standard” 2Gy per day fractionation approaches. A substantial body of evidence suggests that the α/β ratio for prostate cancer is lower than for many cancers, and even for many late responding normal tissues. The α/β ratio is a descriptive value based on the curvature of a cell survival curve [11]. The alpha beta ratio is the dose at which radiation cell killing from linear and quadratic components are equal. In general, early responding tissues, such as mucosa, bone marrow, and skin, have high α/β ratios (on the order of 10) [11]. Late responding tissues, such as brain, spinal cord, muscle, and dermis have very low α/β ratios (on the order of 3) [11]. Tumors can have a range of alpha beta ratios, however certain histologies, such as prostate cancer, melanoma, and sarcoma, have been described to have very low α/β ratios. The clinical implication of this information is that tumors with low α/β ratios, such as prostate cancer, should respond favorably to large dose per fraction (hypofractionated) approaches.

Although much of this work in defining alpha beta ratios was initiated in vitro, studies of patients treated with radiotherapy have been used to confirm that the α/β ratio of prostate cancer is indeed low [12]. These findings have been used as the rationale for developing hypofractionated regimens for the treatment of patients with previously untreated prostate cancer [13]. Several randomized trials of hypofractionated radiotherapy compared to standard fractionation in patients with intact prostates have suggested that this approach is effective and well tolerated [14-16]. Mathematical calculations can be used to determine isoeffect levels (biologically equivalent dose) using the formula $BED_x = TD(1+x/[\alpha/\beta])$, where x is the fraction size, TD is the total dose delivered, and α/β is the ratio of the tissue of interest. Few, if any, normal tissues have an α/β ratio less than 3. Thus, by using the α/β ratio of 3 to drive choice of an appropriate hypofractionated regimen, tissues with higher α/β ratios may actually benefit from hypofractionation as the BED of these fractionation regimens may be biologically “less dose” when considering a α/β higher than 3. For example, delivering 68.4 Gy in 2 Gy fractions is equivalent to delivering 56.4 Gy in 2.82 Gy fractions if using an α/β of 3(prostate cancer, late responding normal tissues). The similar regimen delivers a dose biologically equivalent to 60.25 Gy in 2 Gy fractions (α/β ratio of 10, early responding tissues). Thus, the more sensitive normal tissues receive a reduced dose biologically while the tumor receives a biologically equivalent dose.

There is substantial interest in the use of hypofractionated radiotherapy for prostate cancer, largely because of the prevailing thought that prostate cancer exhibits a low α/β ratio. In addition, hypofractionated therapies are of increasing interest given enhanced conformality of radiation

treatments and enhanced convenience for patients. The vast majority of data evaluating outcomes of hypofractionated radiotherapy in the treatment of prostate cancer has been developed in the setting of an intact prostate (no prior surgery). The doses used in the setting of radiotherapy are substantially higher than those used in the post-prostatectomy setting (79-82 Gy compared to 66-72 Gy). Additionally, the volumes treated in the intact prostate setting are generally smaller than those treated in the post-prostatectomy setting. Regardless, these studies do provide information on the efficacy and tolerability of hypofractionated radiotherapy in a similar region of the body. In many cases, these regimens, although hypofractionated compared to the current standard, were substantially less hypofractionated than the regimen proposed herein.

A recent multi-center randomized trial (PROFIT) evaluated the efficacy of hypofractionated radiation in patients with intermediate risk localized prostate cancer in which 1,206 patients were randomized to conventional dosing (78 Gy in 2 Gy fractions) versus hypofractionated radiation (60 Gy in 3 Gy fractions) [17]. At a median follow-up of 6 years, the biochemical disease free survival was 85% in both arms (the study endpoint was non-inferiority), with no significant differences in late > Grade 3 genitourinary or gastrointestinal toxicity. Similarly, RTOG 0415 enrolled 1,115 men with low to intermediate risk prostate cancer to 73.8 Gy in conventional fractionation or 70 Gy in 2.5 Gy fractions. At a median follow-up of 5.8 years, there were more grade 2 toxicities in the hypofractionation arm, but grade 3 toxicities were similar. In this trial, the moderate hypofractionation regimen was also found to be non-inferior [18]. In the CHHiP trial, 3,216 men with intermediate risk prostate cancer were randomized to 74 Gy in conventional fractionation compared to 57-60Gy in 3 Gy fractions [14]. At 62 months of follow up, the hypofractionated regimen was not inferior. In this trial, there were more acute toxicities in the hypofractionated group and more late toxicity in the conventionally fractionated group. The HYPRO trial assessed 64.6 Gy in 3.4 Gy fractions (3 times per week) compared to 78 Gy standard fractionation. Other trials assessing superiority of hypofractionated radiotherapy versus conventionally fractionated radiotherapy in the setting of intact prostate have not found evidence of superiority [19-21]. As these dosing regimens are calculated for estimated equivalence of tumor control, these are findings are not particularly surprising.

In the post-prostatectomy setting, NRG Oncology has recently activated a trial of hypofractionated radiotherapy post-prostatectomy (NRG GU003). In this trial, 282 patients will be randomized to hypofractionated radiotherapy or conventionally fractionated radiotherapy (66.6 Gy in 1.8 Gy fractions versus 62.5 Gy in 2.5 Gy fractions). In the RTOG trial, the hypofractionated arm also includes a dose escalation component (the entire prostate bed receives the hypofractionated dose which is biologically equivalent to an escalated dose). Supporting studies for this trial included a series from the University of Wisconsin, which evaluated 65 Gy in 2.5 Gy fractions to the prostate bed with a resulting 4 year progression free survival of 67% at a median follow up of 34 months [22]. In this trial, late toxicity was highly favorable compared to historical series.

This trial is substantially different from published series in that it is not “moderate” hypofractionation. This approach is substantially more hypofractionated compared to regimens previously investigated in this context and much more in line with modern hypofractionated SBRT approaches that have been used for radiation of the intact prostate. Second, this trial includes an escalation component in which the imaged tumor is escalated while dose to the remaining prostate bed is reduced to a dose that is biologically equivalent to a “microscopic”

radiotherapy dose. Finally, the trial attempts to integrate novel quality of life, biomarker, and correlative endpoints to further explore the effects of this rapid treatment.

1.2.3 Quality of life after salvage radiation

Altering the dose per fraction given during radiation treatments not only impacts malignant cells, but also surrounding normal tissues. As the dose per fraction received by these tissues changes, so also may the rate of acute and late toxicity. Therefore, assessment of acute and late toxicity and resultant quality of life effects is an important component of outcomes assessment in altered fractionation radiation regimes. Validated measures such as the EPIC-26, AUA, and SHIM are key in assessing both objective and subjective patient reported outcomes post-treatment. They focus on bowel and urinary toxicity, as well as sexual and erectile function, which can all be negatively affected by treatments for prostate cancer, in both the upfront and salvage settings [23, 24].

While altered fractionation may have a potential benefit in tumor cell kill, novel fractionation modalities must also address patient quality of life particularly with adjuvant and salvage radiation therapy post-prostatectomy [25, 26]. Decision regret after prostate cancer is a recognized phenomenon occurring in 10-20% of patients after upfront treatment [27-30]. Decision regret has been associated with time since treatment, toxicities, and patient demographics [29-31]. Increased levels of regret have been associated with bowel or bladder toxicity from, but independent of, treatment modality [24, 27, 28], and may be more common in men who experience PSA recurrence or metastatic disease [31]. Despite these efforts, a comprehensive schema of factors involved in decision regret has not yet been established. It is important to explore factors such as mood and patients' views on their disease in order to better understand the components of decision regret, and how they can best be mitigated. Uniquely in this research, we will address patients who have options for curative intent salvage treatments, rates of decision regret post-prostatectomy, and if subsequent regret can be mitigated by effective salvage therapies.

The questionnaires used in this trial are:

- The Expanded Prostate Cancer Index Composite (EPIC-26) is a prostate cancer health-related quality of life (HRQOL) patient self-administered instrument that measures urinary, bowel, sexual, and hormonal symptoms related to radiotherapy and hormonal therapy. The EPIC-26 was developed from the 50-item EPIC questionnaire and was validated using question responses from 252 subjects who had undergone brachytherapy, external beam radiotherapy, or prostatectomy for prostate cancer. A high correlation was observed between the EPIC-50 and EPIC-26 versions for the urinary incontinence, urinary irritation/obstruction, bowel, sexual, and vitality/hormonal domain scores (all $r >= 0.96$). The correlations between the different domains were low, confirming that EPIC-26 retained the ability to discern the distinct HRQOL domains. The internal consistency and test-retest reliability for EPIC-26 (Cronbach's alpha $>= 0.70$ and $r >= 0.69$, respectively for all HRQOL domains) supported its validity. EPIC-26 has been used in multiple RTOG protocols and phase II publications for hypofractionated radiotherapy to the prostate.
- Sexual Health Inventory for Men (SHIM) is a prostate specific questionnaire for assessment of erectile dysfunction. Initially derived from the IIEF, a shortened version to six questions the IIEF-6 or SHIM was created for increased usability in the clinic.

- American Urologic Association Symptom Index Score (AUA-SI) has been established as a measure of radiation morbidity in patients treated for prostate cancer with respect to urinary function and is used routinely as the basis for treatment decisions. Moderate agreement was observed between EPIC domains and the American Urological Association Symptom Index (AUA-SI), providing criterion validity without excessive overlap.
- PROMIS – Depression SF4a: The PROMIS Depression item bank assesses self-reported negative mood (sadness, guilt), views of self (self-criticism, worthlessness), and social cognition (loneliness, interpersonal alienation), as well as decreased positive affect and engagement (loss of interest, meaning, and purpose). The depression short forms are universal rather than disease-specific. All assess depression over the past seven days. PROMIS instruments are scored using item-level calibrations.
- PROMIS – Anxiety SF4a: The PROMIS Anxiety item banks assess self-reported fear (fearfulness, panic), anxious misery (worry, dread), hyperarousal (tension, nervousness, restlessness), and somatic symptoms related to arousal (racing heart, dizziness). Anxiety is best differentiated by symptoms that reflect autonomic arousal and experience of threat. Only one behavioral avoidance item is included in the adult item bank; therefore, behavioral fear avoidance is not fully evaluated. The anxiety measures are universal rather than disease-specific. All assess anxiety over the past seven days.
- PROMIS – Psychosocial Impact Positive SF 4a assess positive psychosocial (emotional and social) outcomes of illness, previously conceptualized in various ways including post-traumatic growth, benefit-finding, and meaning making. Positive Illness Impact refers to positive psychosocial outcomes of illness that can occur as a result of confrontation with one's mortality, such as greater life appreciation, interpersonal relationships and personal resources.
- Decision Regret Scale (DRS) is a 5-item scale measuring distress or remorse after a health care decision. It has been psychometrically validated in the prostate cancer population. The score correlated with satisfaction with the decision ($r=-0.40$ to -0.60), decisional conflict ($r=0.31$ to 0.52), and overall rated quality of life ($r=-0.25$ to -0.27).

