3 STUDY IMPLEMENTATION

3.1 STUDY DESIGN

There will be two Arms in this trial. Arm 1 includes patients with rising PSA after prostatectomy for whom recurrent tumor has been visualized in the pelvis, providing a target for dose escalation. Arm 2 includes patients with rising PSA with no visualized tumor on imaging or patients with indications for adjuvant radiation after prostatectomy. Patients in whom MRI is contraindicated may enroll on Arm 2 if no evidence of disease is noted on other imaging modalities.

In Arm 1 radiation will be delivered to an escalated dose to areas of recurrent prostate cancer identified on imaging and a reduced dose will be delivered to the entire prostate bed.

In Arm 2 radiation will be delivered to the prostate bed only in patients for whom no recurrent tumor is visualized on imaging or if MRI imaging was contraindicated.

On Dose Level 1 treatments will be delivered in 20 fractions (approximately 4 weeks), on Dose Level 2 - in 15 fractions (approximately 3 weeks), on Dose Level 3 - in 10 fractions (approximately 2 weeks).

Abbreviated Title: Image guided radiation

Version Date: 06/03/2024

Treatment will be administered in daily fractions Monday through Friday except in the case of machine malfunction or federal holiday.

Daily image guidance with cone beam CT will be preferred. kV/kV imaging is allowed if the Cone beam CT imager is unavailable. An additional post-treatment cone beam CT after each fraction may be obtained to assess intrafraction motion.

Table 1 Fraction Dose Escalation Schedule

	Cohort 1, Arm1: Recurrent tumor visible, prostate bed with integrated boost		Cohort 2, Arm 2: Recurrent tumor NOT visible, prostate bed irradiation only	
Dose level	Dose to prostate bed	Dose to tumor	Dose to prostate bed	Dose to tumor
Level 1: 20 fractions	45.8 Gy in 2.29 Gy fractions	60.4 Gy in 3.02 Gy fractions	56.4 Gy in 2.82 Gy fractions	-
Level 2: 15 fractions	41.85 Gy in 2.79 Gy fractions	54.6 Gy in 3.64 Gy fractions	51.2 Gy in 3.41 Gy fractions	-
Level 3: 10 fractions	36.4 Gy in 3.64 Gy fractions	47.1 Gy in 4.71 Gy fractions	44.2 Gy in 4.42 Gy fractions	-

Serial PSA and serial correlative studies will be collected for two years post-treatment.

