8.4.3 Analysis of the Secondary Endpoint(s)

- Define the toxicity profile of image-guided, focally dose escalated prostate bed radiation in patients with a local or regional recurrence of prostate cancer after prostatectomy. All AEs except grade 1 with attribution to protocol treatment will be collected in tabulated way and analyzed.
- The rate of PSA control (biochemical progression free survival, bPFS) will be estimated by the Kaplan-Meier survival analysis and effects of clinical variables on bPFS will be assessed by the Cox proportional hazards model.
- The quality of life scores will be summarized at baseline and for each visit. Linear mixed effects model will be used to model quality of life scores at baseline and during and after treatment in which random intercept and random slope are used to account for patient-specific trajectory of quality of life scores. Changes of quality of life scores during and after treatment will be calculated from the estimated linear mixed effect model. The

similar analytical approach will be performed for depression scores and correlated with quality of life scores.

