8.4.5 Exploratory Analyses

- Evaluate decision regret at the time of enrollment and at the end of follow up relating to the primary treatment for prostate cancer to determine if successful salvage mitigates decision regret. The percentage of patients scored as having decision regret will be compared to the percentage of patients not exhibiting decision regret (regarding the initial surgery). It is hypothesized the effective salvage therapy will mitigate decision regret expressed at the time of enrollment.
- Explore candidate biomarkers of radiation toxicity in blood and urine of patients receiving image-guided, hypofractionated, focally dose escalated post-prostatectomy radiation. Protein and metabolic biomarkers will be assessed in collected specimens.
- Explore MRI imaging parameters of erectile tissues in regards to testosterone and erectile dysfunction. MRI imaging of erectile tissue will be compared to evaluate for changes in volume and tissue characteristics after radiotherapy.
- To compare dosimetry of standard compared to biological optimization algorithms for treatment planning of post-prostatectomy radiation. Treatment planning will be optimized

with both approaches to allow comparison of normal tissue complication probability curves. Results will be reported in a descriptive fashion.

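### The regret analysis in 8.4.5 cannot address its own question about successful salvage: it includes adjuvant men with no recurrence to salvage and uses no salvage outcome

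*Combined protocol and SAP*

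**What the plan says.** Section 1.2.3 gives the background. "Decision regret has been associated with time since treatment, toxicities, and patient demographics"; the text adds bowel and bladder toxicity in particular, and says that regret "may be more common in men who experience PSA recurrence or metastatic disease". Mood and views of the disease are put forward as things to "explore factors such as mood and patients' views on their disease in order to better understand the components of decision regret". The section then frames the trial's question as whether regret after prostatectomy can be mitigated by effective salvage.

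The first bullet of 8.4.5 repeats that question and states the analysis: "The percentage of patients scored as having decision regret will be compared to the percentage of patients not exhibiting decision regret", with regret referring to the initial surgery. The hypothesis follows: "It is hypothesized the effective salvage therapy will mitigate decision regret expressed at the time of enrollment". The bullet names no analysis set, PSA outcome or covariate.

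On who is in the trial, section 3.1 says "Arm 2 includes patients with rising PSA with no visualized tumor on imaging or patients with indications for adjuvant radiation after prostatectomy". Section 2.1.1.2 defines the adjuvant group by undetectable PSA with adverse pathology, within 1 year of prostatectomy.

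The one mood analysis that is spelled out is in 8.4.3: a "similar analytical approach will be performed for depression scores and correlated with quality of life scores". It does not mention regret. The Decision Regret Scale, EPIC-26 and PROMIS forms are completed together at baseline and every 6 months to month 24, by English-speaking patients only (3.2, 3.3). Biochemical relapse is a listed data element (6.1.1).

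**The concern.** An analysis of whether successful salvage lowers regret needs three things: men who have something to salvage, a variable that says whether salvage succeeded, and each man's regret before and after. The bullet names two assessment times, but its comparison uses none of the three. Adjuvant men had no detectable recurrence at entry, so successful salvage has no meaning for them, yet nothing keeps them out. They may also differ in time since surgery: they must be within 1 year of prostatectomy, and no such limit is stated for men with detectable PSA. Section 1.2.3 links both recurrence and time since treatment to regret.

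The risk is a published statement about salvage and regret that rests on a comparison unable to bear on it.

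**Working it through.** **1. Question against analysis.**

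- Population: the question concerns men receiving salvage treatment. The bullet takes everyone with a regret score.
- Exposure: the question turns on success of salvage. The bullet has no PSA or relapse variable, although one is collected.
- Outcome: the question is about change from enrollment to the end of follow-up. The bullet compares a percentage with its complement. If p is the proportion with regret, the contrast is p against 1 - p. At the 10-20% regret that 1.2.3 cites, that is 10% against 90%, or 20% against 80%. Neither measures change or involves salvage.
- Factors from 1.2.3: toxicity, time since treatment, recurrence and mood are all absent.

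**2. The plan's sample size.** Section 8.2 gives a maximum of 24 per arm and 48 in all. From 3.1.2: 3 dose levels x 6 + 6 in expansion = 24; 24 x 2 arms = 48. This reproduces. No size is given for the regret analysis.

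**3. Men with regret at entry.** "Decision regret after prostate cancer is a recognized phenomenon occurring in 10-20% of patients after upfront treatment" gives 48 x 0.10 = 4.8 to 48 x 0.20 = 9.6 men. The rate may be higher here, since 1.2.3 suggests more regret after recurrence. For scale, exact 95% intervals are 3.5% to 22.7% for 5 of 48 and 10.5% to 35.0% for 10 of 48. One model of yes/no regret on four factors (toxicity, time, recurrence, mood) would have 4.8/4 = 1.2 to 9.6/4 = 2.4 regretters per factor, which is too few to fit.

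**4. A paired yes/no test.** If k men lose regret and none gain it, exact McNemar gives p = 2 x 0.5^k: 0.0625 for k = 5 and 0.031 for k = 6. So at least 6 men must have regret at entry. The adjuvant share is an assumption, shown over a range:

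| Adjuvant share (assumed) | Salvage men | Regretters at 10% / 20% | Chance of 6 or more at 10% / 20% |
|---|---|---|---|
| 0% | 48 | 4.8 / 9.6 | 0.35 / 0.94 |
| 25% | 36 | 3.6 / 7.2 | 0.15 / 0.75 |
| 50% (all of Arm 2) | 24 | 2.4 / 4.8 | 0.03 / 0.34 |

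This favours the change in score with an interval over a test of percentages.

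**5. Splitting by PSA control.** The précis cites control in about 75% with standard treatment, with no time point. At 48 men that is 36 controlled and 12 failed; at 36 salvage men, 27 and 9; at 24, 18 and 6. The failed group is small in every case.

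**6. Men who fail.** Section 3.7.2 lists recurrence as an off-study criterion, so men whose salvage fails may have no final score. Illustration with assumed values: regret of 30% in the 25% who fail, 10% in the rest, and no man changing. Baseline regret is 0.25 x 0.30 + 0.75 x 0.10 = 15%. If only controlled men are scored at the end, it reads 10%. The drop comes entirely from who is left.

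**7. Power for the associated factors.** Section 1.2.3 quotes correlations of the regret scale with satisfaction with the decision (0.40 to 0.60 in size), decisional conflict (0.31 to 0.52) and overall quality of life (0.25 to 0.27). Only the last is near the factors at issue. By Fisher's z, power = Phi(atanh(r) x sqrt(n - 3) - 1.96):

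- n = 40 (assumed), r = 0.25: 0.2554 x 6.083 - 1.96 = -0.41, power 34%.
- n = 40, r = 0.27: 0.2769 x 6.083 - 1.96 = -0.28, power 39%.
- n = 48: 40% and 46%.

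**The case against.** The strongest reply is that this is one exploratory bullet in a phase I trial of at most 48 men, with 5 to 10 expected to report regret, and that the objective does name successful salvage and two assessment times. A sensible analyst would compare the two times and look at PSA status. That limits the importance of the point. It does not repair the bullet, whose stated comparison does neither.

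Second, restriction costs data: step 4 shows how quickly the salvage set shrinks. This stands as a cost. Also, section 1.2.1 says many men with adjuvant indications are monitored instead, so the adjuvant share may be small.

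Third, a reader might infer more than the documents support:

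- That mood and toxicity are established causes of regret. Section 1.2.3 says associated, and mood is only to be explored.
- That toxicity from this radiation pushes up regret and hides a benefit of salvage. Section 1.2.3 describes regret after upfront treatment, and 8.4.5 concerns regret about the surgery; neither says that later radiation toxicity changes it. One-factor models could not separate offsetting effects in any case.
- That every factor is already recorded. Time since prostatectomy is not a listed data element in 6.1.1 and would have to be derived from the history. Under 6.1, after 30 days only serious related events need be recorded, although 3.1.1 has late toxicities followed and scored. EPIC-26 is a partial substitute.
- That PROMIS Anxiety and Positive Impact are orphaned. Appendix B groups the questionnaires as quality-of-life instruments, and 8.4.3 does not list which scores it models, so they may be covered there.

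**Conclusion.** The point holds. As written, the first bullet of 8.4.5 cannot address whether successful salvage mitigates regret: it takes all patients, uses no salvage outcome, and leaves out every factor that 1.2.3 associates with regret or proposes to explore. That adjuvant men are included is inferred from the absence of any restriction.

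The distortion has no documented size. If a share a of men is adjuvant and their regret does not change, the pooled change is (1 - a) times that in salvage men: 75% of it at a = 25%, 50% at a = 50%. Both the share and the zero change are assumptions, so this is only an illustration.

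Two stronger conclusions should be resisted. One is that adding covariates would tie a change in regret to salvage; there is no control group, so even a good analysis stays descriptive. The other is that the trial is large enough to be informative about the associated factors; the nearest quoted correlations give 34-39% power at an assumed 40 men. The consequence is confined to an exploratory objective and leaves the MTD and the secondary endpoints untouched.

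**What to change.** Rewrite the first bullet of 8.4.5 to say:

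- The salvage-and-regret question is limited to men with detectable PSA at entry; adjuvant men are reported separately.
- The summary is the within-patient change in Decision Regret Scale score from enrollment to the end of follow-up, with a 95% CI, tabulated by biochemical control status as defined in 6.3.1.
- EPIC-26 bowel and urinary scores and the PROMIS scores from the same visits are shown alongside, descriptively.
- No causal wording and no power claim.

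The bullet should also state which score counts as final for a man who leaves the study at recurrence, and how many such men have none; otherwise the failed column may be nearly empty. Collecting the scale after recurrence would close that gap but needs a change to the off-study rule in 3.7.2.

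Models of regret on mood or time since surgery, and naming each PROMIS form in 8.4.3, are optional.

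The cost is analysis-plan wording on data already collected. The downside is fewer men in the salvage analysis, by a number the documents do not allow one to state, and imprecise estimates with at most 48 men.
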